## 15 Appendix 3: Treatment guidelines for hyperkalemia (serum potassium greater than or equal to 5.3 mmol/L [mEq/L])

### General principles

Elevation of potassium levels above the predefined values should be repeated and confirmed before any action is taken.

Any patient with a serum potassium  $> 5.3$  mmol/L (mEq/L) at any time after randomization requires the Investigator to confirm the potassium concentration in a non-hemolyzed sample via an immediate repeat lab sample to both the clinic local lab and the study central lab. Regular, repeated checks of potassium concentration (beyond that prescribed in the protocol) should continue until it is clear that the potassium concentration is stable and not rising into the range of concern ( $\geq 5.5$  and  $< 6.0$  mmol/L [mEq/L]) or potential danger ( $\geq 6.0$  mmol/L [mEq/L]).

Patients with elevated potassium value will be managed according to the corrective actions outlined below. Hyperkalemia should be followed until resolution.

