**Table 3-2 Safety monitoring criteria that must be met at Visit 1 (screening), Visit 103 and Visit 199/201**

Parameter	Visit 1 (Screening)	Visits 103 (treatment run-in) and Visit 199/201 (end of treatment run-in/randomization)
Potassium level	K ≤5.2 mmol/L (mEq/L)	K ≤5.4 mmol/L (mEq/L)
Kidney function	eGFR ≥30 mL/min/1.73m 	eGFR ≥25 mL/min/1.73m  eGFR reduction <35% compared to Visit 1
Blood pressure	SBP ≥110 mmHg	No symptomatic hypotension as determined by the investigator and SBP ≥100 mmHg.
AEs or conditions	No conditions that preclude continuation according to the investigator's judgment	No postural symptoms or any AEs that preclude continuation according to the investigator's judgment

AE – adverse event

To assess the patient's eligibility to continue in the study, either local or central laboratory should be used for the assessment of potassium and estimated glomerular filtration rate (eGFR) at Visits 103 and 199/201 (end of treatment run-in visit/randomization). If central laboratory is used, since it may take up to 72 hours to obtain the results, it is recommended that the site take this into consideration when scheduling subsequent study visits, while keeping the patient on the study medication. If a local laboratory is selected, the same samples should also be sent to the central laboratory, while the evaluation should be solely based on the local laboratory results. Patients should NOT enter Visits 103 or 199/201 without evaluating the safety monitoring criteria (Table 3-2).

Down-titration of study drug is not allowed during the treatment run-in period. Patients who are not able to tolerate study drug at the doses prescribed during the treatment run-in epoch will be discontinued.

Investigators may consider adjusting (dose reduced or discontinued) background medications (e.g., diuretic(s), antihypertensive agents, cardiovascular medications such as beta blockers, MRAs, nitrates, etc.) if the study drug is not tolerated (e.g., occurrence of AEs such as hyperkalemia, hypotension, and renal dysfunction) to ensure patients meet the safety criteria in [Table 3-2](#) during the treatment run-in epoch. Patients may be seen at any time for unscheduled visits during the treatment run-in epoch for re-evaluation of safety criteria parameters.

Patients who experience angioedema at any time during the treatment run-in epoch must be discontinued from the study.

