#### **5.5.6 Rescue medication**

Guidance on handling hyperkalemia, hypotension, and renal dysfunction will be provided to investigators (Appendix 3, Appendix 4, and Appendix 5 respectively). Patients may receive open-label ACEis, ARBs or a renin inhibitor during the study ONLY if the study drug has been temporarily or permanently discontinued. If for any reason a patient off study drug has started open-label treatment with an ACEi it must be discontinued  $\geq 36$  hours prior to restarting study drug.

Use of rescue medication must be recorded on the Concomitant medications/Significant non-drug therapies CRF.

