**Table 14-2 Follow up requirements for liver events**

Criteria	Event type	Actions required	Follow-up monitoring
Potential Hy's Law case a	Medically significant	Discontinue the study drug immediately Hospitalize, if clinically appropriate Report to Novartis as an SAE Establish causality	ALT, AST, TBL, Alb, PT, ALP and $\gamma$ GT until resolution c (frequency at investigator discretion)
ALT or AST			
> 8 x ULN	Medically significant	Repeat LFT within 48 hours If elevation persists, discontinue the study drug immediately Hospitalize if clinically appropriate Report to Novartis as an SAE Establish causality	ALT, AST, TBL, Alb, PT, ALP and $\gamma$ GT until resolution c (frequency at investigator discretion)
> 5 to $\leq$ 8 x ULN	Medically significant	Repeat LFT within 48 hours If elevation persists for more than 2 weeks, discontinue the study drug Report to Novartis as an SAE Establish causality	ALT, AST, TBL, Alb, PT, ALP and $\gamma$ GT until resolution c (frequency at investigator discretion)
> 3 x ULN accompanied by symptoms b	Medically significant	Discontinue the study drug immediately Hospitalize if clinically appropriate Report to Novartis as an SAE	ALT, AST, TBL, Alb, PT, ALP and $\gamma$ GT until resolution c (frequency at investigator discretion)

Criteria	Event type	Actions required	Follow-up monitoring
		Establish causality	discretion)
> 3 to ≤ 5 x ULN (patient is asymptomatic)	Adverse event of special interest (AESI)	Central laboratory to report to Investigator & Novartis Repeat LFT once or twice in the week If elevation persists, establish causality	Investigator discretion Monitor LFT within 1 to 4 weeks or at next visit
≤ 3 x ULN (patient is asymptomatic)	N/A	Repeat LFT at next visit	
ALP (isolated)			
> 5 x ULN	Medically significant	Repeat LFT within 48 hours If elevation persists, report to Novartis as an SAE Establish causality	Investigator discretion Monitor LFT within 1 to 4 weeks or at next visit
> 2 to ≤ 5 x ULN (patient is asymptomatic)	AESI	Central laboratory to report to Investigator & Novartis Repeat LFT once or twice in the week. If elevation persists, establish causality	Investigator discretion Monitor LFT within 1 to 4 weeks or at next visit
≤ 2 x ULN (patient is asymptomatic)	N/A	Repeat LFT at next visit	
TBL (isolated)			

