**Serum potassium greater than 5.5 and less than 6.0 mmol/L (mEq/L)**

- Confirm potassium concentration in a non-hemolyzed sample
- Consider down-titration or temporarily discontinue study drug according to investigator medical judgment.
- Apply all measures outlined for serum potassium  $> 5.3$  and  $\leq 5.5$  mmol/L
- Repeat serum potassium measurement after 2-3 days
- If serum potassium  $< 5.5$  mmol/L, consider resumption of study drug at lower dose with repeat potassium within 5 days

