**Serum potassium greater than or equal to 6.0 mmol/L (mEq/L)**

- Immediately discontinue study drug
- Confirm potassium concentration in a non-hemolyzed sample
- Urgently evaluate patient and treat hyperkalemia as clinically indicated
- Apply all measures outlined for serum potassium  $> 5.3$  and  $< 6.0$  mmol/L (mEq/L)

No resumption of study drug without individualized case discussion with and permission from Novartis medical monitor or his/her designee.

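### Appendix 3's rule to confirm raised potassium before acting makes no exception at 6.0 mmol/L or above, where its own action block stops study drug at once

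*Protocol*

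**What the plan says.** Protocol Appendix 3 (Section 15) has two parts.

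- **General principles.** The opening sentence reads "Elevation of potassium levels above the predefined values should be repeated and confirmed before any action is taken". For any value above 5.3 mmol/L after randomization, the investigator confirms the value "via an immediate repeat lab sample to both the clinic local lab and the study central lab". The passage names 6.0 or above as the range of potential danger. It ends with a pointer: "Patients with elevated potassium value will be managed according to the corrective actions outlined below".
- **Corrective actions.** There are three blocks by level. The top block, for 6.0 mmol/L or above, starts with "Immediately discontinue study drug". Confirmation comes second and urgent evaluation and treatment third. Restarting drug needs the medical monitor's permission.

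Section 5.5.6 makes this appendix the working reference for sites: "Guidance on handling hyperkalemia, hypotension, and renal dysfunction will be provided to investigators".

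**The concern.** The opening sentence covers every elevation and every kind of action. The top block orders an action before confirmation. A site with a first reading of 6.0 or above therefore has one instruction to wait for the repeat and another to stop drug now, in the range where the order matters most.

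Taken literally, the general rule would hold back the urgent evaluation and treatment in the top block as well as the drug stop. The stake is clear safety instructions to sites. It does not touch the endpoint, the analysis or the sample size.

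**Working it through.** No plan figure has to be reproduced. The check compares texts.

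**Step 1. Compare each block with the general rule (confirm, then act).**

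| Serum potassium (mmol/L) | First step in the block | Place of confirmation | Fits the rule? |
|---|---|---|---|
| above 5.3, up to 5.5 | confirm | first | yes |
| above 5.5, below 6.0 | "Confirm potassium concentration in a non-hemolyzed sample" | first; the drug change that follows is at the investigator's discretion | yes |
| 6.0 or above | "Immediately discontinue study drug" | second | no |

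The conflict sits in the top block and nowhere else.

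**Step 2. Look for a sentence that settles the order.**

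- The General principles send patients to the blocks but do not say that a block overrides the confirm-first rule.
- Section 5.5.5 lets the investigator reduce the dose at any time, as far as a temporary stop, on his or her own judgment.
- Section 5.6.2 requires treatment to be stopped when the investigator believes that continuing would harm the balance of risk and benefit.
- Section 11.1 expects immediate safety action even where it departs from the protocol.

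These provisions allow a site to stop drug. None of them changes the opening sentence of Appendix 3.

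**Step 3. Infer the intent.** Appendix 2 shows how the protocol writes a repeat-first condition when it wants one. For ALT or AST above 8 times the upper limit of normal, Table 14-2 says "Repeat LFT within 48 hours If elevation persists, discontinue the study drug immediately". The top potassium block has no such condition. Together with the pointer to the blocks, this makes stop-first the likely meaning.

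**Step 4. Where it can arise.** It can arise at any potassium reading of 6.0 or above after randomization. In Table 6-1, the visible abbreviated panel, which includes potassium, is scheduled at Visits 202, 203, 207 and 211 (weeks 13, 26, 78 and 130). That is 1 + 1 + 1 + 1 = 4 readings per patient who attends those visits. It is a floor, because some laboratory rows are redacted and unscheduled tests also occur. The documents give no rate of readings at 6.0 or above, and none is assumed.

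**The case against.** The strongest reply is that the text nearly resolves itself. A specific block normally governs over a general principle. The top block is unconditional and says to act at once. The appendix is titled as guidelines, and its opening sentence is phrased as a recommendation. With Sections 5.5.5, 5.6.2 and 11.1, a site has ample authority to stop drug at 6.0 or above. All of this stands, and it limits the practical risk. It does not remove the contradiction: a site should not have to work out which sentence prevails, or rely on the deviation clause, to follow the protocol's own action block.

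A reader might go further and infer a delay on drug of up to three days. The General principles ask for the repeat at both laboratories without saying which result confirms, and Section 3.1 says "If central laboratory is used, since it may take up to 72 hours to obtain the results". The documents do not support that inference. The turnaround is stated for eligibility checks in the run-in and at randomization. The same paragraph bases the evaluation solely on the local result when a local laboratory is chosen. Appendix 3 asks for an immediate local repeat. A site would also have to disregard the top block altogether. No delay or count of doses is claimed here.

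A reader might also see an error at exactly 5.5 mmol/L, which the General principles put in the range of concern but the headings put in the lowest action block. The blocks are contiguous, so 5.5 has one set of actions. The middle block resumes drug only below 5.5, which agrees with the General principles as written. Moving that boundary would create a new mismatch.

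**Conclusion.** The conflict is real and confined to readings of 6.0 mmol/L or above. There the general rule and the top block cannot both be followed as written, and no visible text says which prevails. Stop-first is very probably what was meant, so sites may act differently, but nothing shows that they will.

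This is a minor correction of safety wording. It has no effect on any analysis: Section 9.4.2 counts on-treatment data regardless of interruption.

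One caveat applies. Section 7.1 places laboratory alert ranges in Appendix 1, which is not in the text available for review, so the finding that no exception exists covers only the visible text.

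**What to change.** Keep the opening sentence of the Appendix 3 General principles and add at its end: *except at 6.0 mmol/L or above, where study drug is stopped immediately, the patient is urgently evaluated and treated, and the value is confirmed in parallel.* Leave the block for 6.0 or above unchanged, including its restart condition. Leave the 5.5 boundary alone. The appendix heading includes 5.3 itself while the text starts above 5.3. That is clerical and can be tidied in the same amendment.

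The cost is one clause in one appendix. Section 11.1 requires a written amendment approved by the sponsor, the ethics committees and, where required, health authorities. More than 100 centers are planned (Section 4) and would need to be told. No visit, procedure, patient or analysis is added.

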### Corrective action for management of hyperkalemia

#### Serum potassium greater than 5.3 and less than or equal to 5.5 mmol/L (mEq/L)

- Confirm potassium concentration in a non-hemolyzed sample
- Reinforce low potassium diet and restriction of food/drinks with high potassium content (e.g., orange juice, melon, bananas, tomatoes, dried fruits, potatoes, low-salt substitutes, tomatoes, coffee, etc.)
- Correct metabolic acidosis if necessary.
- Review medical regimen (including dietary supplements and over-the-counter medications) for agents known to cause hyperkalemia. Consider reduction in dose or discontinuation of these agents:
  1. MRAs (if they are believed to be the most likely cause of hyperkalemia)
  2. Potassium-sparing diuretics (e.g., amiloride and triamterene) including in combination products with thiazide or loop diuretics
  3. Potassium supplements, e.g., potassium chloride
  4. Salt substitutes
  5. Non-steroidal anti-inflammatory drugs (NSAIDs)
  6. Cyclo-oxygenase-2 (COX-2) inhibitors
  7. Trimethoprim and trimethoprim-containing combination products, such as Bactrim® and Septra® (trimethoprim/sulfamethoxazole fixed combination)
  8. Herbal Supplements:  
For example, Noni juice, alfalfa (*Medicago sativa*), dandelion (*Taraxacum officinale*), horsetail (*Equisetum arvense*), nettle (*Urtica dioica*), milkweed, lily of the valley, Siberian ginseng, hawthorn berries

- Assess patient for dehydration or any condition that could lead to dehydration (e.g., diarrhea, vomiting) and/or hypovolemia and initiate appropriate corrective measures of rehydration.
- Repeat serum potassium measurement within 3 to 5 days
- If serum potassium remains  $> 5.3$  and  $\leq 5.5$  mmol/L (mEq/L), regularly monitor serum potassium levels to ensure stability (suggested once monthly)
- Consider down-titration of study drug, according to investigator's medical judgment.

**Serum potassium greater than 5.5 and less than 6.0 mmol/L (mEq/L)**

- Confirm potassium concentration in a non-hemolyzed sample
- Consider down-titration or temporarily discontinue study drug according to investigator medical judgment.
- Apply all measures outlined for serum potassium  $> 5.3$  and  $\leq 5.5$  mmol/L
- Repeat serum potassium measurement after 2-3 days
- If serum potassium  $< 5.5$  mmol/L, consider resumption of study drug at lower dose with repeat potassium within 5 days

**Serum potassium greater than or equal to 6.0 mmol/L (mEq/L)**

- Immediately discontinue study drug
- Confirm potassium concentration in a non-hemolyzed sample
- Urgently evaluate patient and treat hyperkalemia as clinically indicated
- Apply all measures outlined for serum potassium  $> 5.3$  and  $< 6.0$  mmol/L (mEq/L)

No resumption of study drug without individualized case discussion with and permission from Novartis medical monitor or his/her designee.

## 16 Appendix 4: Guidelines for the management of blood pressure

### Guidelines

1. Investigator should monitor BP closely
2. If symptomatic hypotension occurs:
  - a. Correct any treatable cause, e.g. hypovolemia
  - b. If hypotension persists, any antihypertensive drug such as diuretics, calcium channel blockers (CCBs), nitrates, beta blockers, aldosterone antagonists and  $\alpha$ -blockers, should be down-titrated or stopped first before down-titration of the study drug is considered. Any non-antihypertensive drug (such as nitrates) should be considered for down-titration prior to study drug as determined by the best judgment of the investigator.
  - c. If hypotension persists, the study drug should be down-titrated or even temporarily withdrawn. The dose re-challenge and medications adjust guidelines described in [Section 5.5.5](#) should be adhered to as much as possible.

## 17 Appendix 5: Guidelines for the management of renal dysfunction

### General principles:

Glomerular filtration rate in HF patients depends on intrinsic renal function and on a balance between afferent and efferent glomerular arterial tonicity. This tonicity is partly regulated by a stimulation of angiotensin II and could be affected by either study drug. Moreover, renal dysfunction may develop or may deteriorate in some patients after study drug administration. These recommendations have been developed to guide the investigators in managing patients with renal dysfunction after randomization.

### Two types of response to serum creatinine increase are described:

#### Surveillance situation

If, at any time after randomization, eGFR decreases by  $\geq 25\%$  from baseline (Visit 1) (or if serum creatinine concentration increase to 2.5 mg/dL [221  $\mu\text{mol/L}$ ]), the investigator will check for potentially reversible causes of renal dysfunction such as:

- Non-steroidal anti-inflammatory drug intake, antibiotics, or other treatments known to affect creatinine
- Volume decrease, including that resulting from excessive dosing of diuretics
- Urinary infection
- Urinary tract obstruction
- Study drug

#### Action situation

If a patient's eGFR decreases by  $\geq 40\%$  from baseline (Visit 1) (or if serum creatinine concentration rises above 3 mg/dL (265  $\mu\text{mol/L}$ )), the investigator will check for potentially reversible causes of renal dysfunction (see above).

The investigator may consider down-titration of study drug. If the investigator judges that study drug has to be stopped, he/she will have to contact the Novartis medical monitor or his/her designee. Thereafter, serum creatinine assessments will have to be repeated at least each week until levels return to acceptable values. If study drug was stopped, every effort will be done to restart it again, according to clinical conditions.

Clinical Development

LCZ696/Entresto®

CLCZ696B2320 / NCT02884206

A multicenter, randomized, double-blind, active-controlled study to evaluate the effects of LCZ696 compared to valsartan on cognitive function in patients with chronic heart failure and preserved ejection fraction

Statistical Analysis Plan (SAP)

[figure not shown]
Authors: Trial Statistician, 

Document type: Amended SAP Documentation

Document status: Version 5.0

Release date: 30-Jun-2022

Number of pages: 57

Document History – Changes compared to previous final version of SAP

Date	Time point	Reason for update	Outcome for update	Section and title impacted (Current)
1-Nov-2016	Prior to FPFV	Creation of final version	N/A - First version	NA
31-Jan-2018	After protocol amendment V02	Incorporate updates in protocol amendments V01 and V02 into SAP	Amendment Version 02	
1. Sections 2.5 and 2.6: Protocol amendment V01&V02 updated the inclusion/exclusion criteria in terms of cerebrovascular disease burden at screening. However, this is an important prognostic factor of cognitive functions. Therefore, the statistical analyses of primary and secondary objectives are updated to include this factor in the analyses. Appendix 5.4 and Table 5-3 are added to explain how cerebrovascular disease burden score is calculated.2. Minor text edits to make contents clear, including correction of typo(s).
(1) Section 2.1.1: Randomized treatment epoch added as alias double-blind phase;(2) Section 2.2: Appendix 5-3 instead of 5-5;(3) Section 2.10: 2.12 instead of 3.13;(4) Section 2.11: Pet imaging substudy instead of Full analysis set;(5) Section 2.12: Pet imaging substudy instead of Full analysis set;(6) Section 2.13: Pet imaging substudy instead of Full analysis set;(7) Appendix 5.2: minor updates.3. Update subgroup categories in Section 2.2.1 :
(1) Add new countries in the region subgroup;

Date	Time point	Reason for update	Outcome for update	Section and title impacted (Current)
				
 (2) Update APOE4 category; (3) Add baseline cerebrovascular disease burden subgroup due to protocol amendment. (4) In Table 2.1: MMSE at randomization is used to define subgroup in order to be consistent with MMSE randomization stratification factor.
				4. Section 2.3.2 : correct APOE4 summary at randomization baseline instead of screening.
				5. Section 2.3.3 : remove dementia from protocol solicited medical history summary to be consistent with CRF. Remove medical history (MH) by subgroup summary. MH is only summarized by treatment group.
				6. Section 2.4.1 : update formula to be more clear and consistent with Paragon.
				7. Section 2.4.2 : 
 (1) Update ATC WHO Drug version; (2) Category “HF medications” removed to be consistent with Perspective CRF; (3) AD/CI Concomitant medications at randomization summary removed due to randomized patients should not be on these medications.
				8. Section 2.5.1 : 
 (1) formula and text are updated to make it more clear in terms of missing values. (2) Typo “DECT” is corrected to “DET”.
				9. Removed “Assessments at unscheduled visit remapped to the missing scheduled visit

Date	Time point	Reason for update	Outcome for update	Section and title impacted (Current)
				
assessments within a pre-specified window” due to no such unsheduled assessment.
 
(1) Section 2.6.3;
 
(2) Section 2.7.1.1;
 

 
10. Section 2.7.1.1: Add sensitivity analysis for randomization stratification factor “baseline amyloid status”. Qualitative (Visual) assessment method is used to determine the status (positive/negative) and is controlled as a factor in the SUVr analysis ANCOVA model. The baseline amyloid status based on quantitative SUVr cutoff will replace the qualitative baseline amyloid status in the analysis.
 
11. Table 2-6 is updated
 
(1) to be consistent with data collection;
 
(2) SBP 100 mmHg cutoff for HFpEF.
 
12. Sensitivity for mis-stratification of age and MMSE are added for analyses related primary and secondary objectives.
 
13. Section 2.7.4:
 

 
(2) Update text related to Liver enzymes to be consistent with LCZ696 program analysis.

20-May-2021	May-2021	1. To amend Table 5-1 : the protocol deviations leading to exclusion of subjects from analyses for		
1. Table 5-1 in Appendix 5.3
 
(1) Remove 3 deviations from the table: INCL03, TRT06, TRT08;
 
(2) Update 2 deviation ID: OTH03 to OTH09, OTH11 to OTH08.

[figure not shown]
[figure not shown]
Date	Time point	Reason for update	Outcome for update	Section and title impacted (Current)
		the following reasons: (1) APOE4 is covered under study consent, therefore INC03 is not applicable. In addition, TRT06 and TRT08 is removed due to no such PD existed; (2) Deviation ID is updated.		
		2. To address missing assessments due to Covid-19 pandemic.		2. Additional analyses are added to address assessments scheduled to be taken place on/after 1-Mar-2020 but are missing due to potential COVID pandemic impact: (1) Allow wider assessment window for SUVR assessments in PET sub-study, [REDACTED] The added analyses are provided in Sections 2.7.1.1 and 2.12.1, respectively. (2) An indicator variable, IND _{miss} , if patient had a missing assessment(s) on/after 1-Mar-2020 is created separately for the following endpoints: CogState GCCS, cortical composite SUVR, [REDACTED] Additional supportive analysis with IND _{miss} and IND _{miss} -by-treatment fixed-effect factors are added to the analyses described in Sections 2.5.3, 2.7.1.1, and 2.12.1 for CogState GCCS,

Date	Time point	Reason for update	Outcome for update	Section and title impacted (Current)
		
3. To address possible non-convergence issue for MMRM ANCOVA model.
		
[REDACTED] and cortical composite SUVR, respectively to assess if there is a shift in the change from baseline for those who have missing assessment(s) during COVID-19 pandemic.
 
3. If convergence is not achieved for MMRM ANCOVA models, unstructured (UN) covariance matrix used in MMRM model will be replaced by compound symmetry (CS) in order to achieve model convergence. If convergence issue remains, cerebrovascular disease burden variable will be further removed in order to achieve model convergence. Changes are made in the following sections:
 
(1) Section 2.5.2 for primary analysis;
 
(2) Section 2.5.5 for sensitivity analysis of primary analysis;
 
(3) Sections 2.7.1 and 2.7.1.1 for SUVR analyses;

		
4. Per-protocol set 2 and PET substudy set
		
[REDACTED]
 
4. (1) Per-protocol set 2 and PET substudy set is added in Section 2.2;
 
(2) One supportive analysis based on PPS2 is added in Section 2.5.4 and Table 2-3.
 
(3) Wordings related to non-missing baseline in PET substudy set is added in Sections 2.7.1 and 2.12.1.

		
5. Minor wording edits.
 
Protocol amendment 2.0 is in effect when this SAP amendment takes place.
		
5. Minor wording edits:
 
(1) One abbreviation Alzheimer's disease (AD) is added to the list.
 
(2) Section 2.4.1: (1) handling of overlapping start and end dates when calculating exposure duration; (2)

Date	Time point	Reason for update	Outcome for update	Section and title impacted (Current)
				
replace by visit with overall compliance summary during randomized treatment epoch;
 
(3) Section 2.4.2: update the version of NovDTD that will be used in CSR.
 
(4) Section 2.5.1: Z_{CPAL} is among the negative sign tasks in the standardized Z scores;
 
(5) Section 2.5.2: visit-by-baseline GCCS;
 
(6) Table 2-3 and 2-4: MNAR acronym footnote;
 
(7) Section 2.5.5: treatment-by-visit.
 
(8) Sections 2.7.1 and 2.7.1.1: analyses will be performed in the Safety set who participate in the PET image substudy “and with non-missing baseline”.
 
(9) Section 2.7.2.1: update the version of case retrieval strategy that will be used in CSR.

				
10-Jun-2022	10-Jun-2022	1. Update Cohen’s D calculation with 95% confidence interval		Cohen’s D and corresponding 95% CI calculations are updated in Section 2.5.2 . Reference Cumming and Finch 2001 is added.
		2. Additional imputation details are provided for tipping point analysis of missng GCCS		SAS programming details are provided for imputing missing GCCS in tipping point analysis of Section 2.5.5 .
		3. Changes are made in the model assumption in the joint model approach of GCCS sensitivity analysis to be consistent with original paper (Vonesh et al 2006)		(1) Covariance matrix of measurement error $e_i(t)$ in joint model approach of Section 2.5.5 is updated to diagonal matrix with common variance σ_e^2 on the diagonal elements and no correlations between time points.

Date	Time point	Reason for update	Outcome for update	Section and title impacted (Current)
		4. Due to very limited patients with positive baseline amyloid status and convergence issue, the imputation model used in change from baseline in SUVr is updated.		(2) Section 2.5.5 Joint Model approach : A constant baseline hazard function over time is used in the time to starting AD or CI related medications due to limited such events over study duration. An exponential regression instead of Cox proportional hazard is fitted.
		5. Details are added in safety related sections after dry run review.		Section 2.7.1 : (1) There are very limited patients with positive baseline amyloid status, and imputation cannot be done for this stratum. Therefore, baseline amyloid status is included in the imputation model as factor instead. (2) SAS proc MCMC programing detail is provided. Section 2.7.2 : (1) specify analysis set for run-in epoch and double-blind randomized treatment epoch.
				 Section 2.7.3 : Remove “confirmed by adjudication committee” because death is not adjudicated.
		6. Visits numbers are updated in plasma Aβ1-40 to be consistent with		 Section 2.11 : Week 13, 52, 104 and Week 156 are the post-baseline scheduled visits for plasma Aβ1-40 assessments.

Date	Time point	Reason for update	Outcome for update	Section and title impacted (Current)
		protocol assessment schedule Table 6-1.		Analysis set for plasma Aβ1-40 is PET substudy set with non-missing baseline.
		7. Updates related to protocol deviations impacting analysis sets		
(1) Deviation ID OTH02 in Table 5-1: Site has been closed down for GCP reasons are not excluded from Safety set (SAF).
 
(2) Per clinical review: EXCL01, EXCL13, EXCL23, EXCL24, EXCL25, EXCL26, EXCL27, TRT07 are removed, and OTH21 is added in Table 5-1.
 
(3) Table 5-2 is updated to be aligned with Table 5-1.

		8. Additional statement for different endpoints PET substudy set		
Section 2.2: Separate flag will be create for different endpoint due to non-missing baseline condition for PET substudy set

		9. Remove subgroup analysis for disposition related summary, add 3 subgroups for CogState GCCS, minor update to NYHA category, and remove Central America from Latin America definition		
Table 2-1: (1) CTT reviewed and decided to remove the subgroup analyses of disposition from CSR; (2) Randomization baseline SBP ≤140 and >140 mmHg subgroup, Age < 65 and ≥ 65 subgroup, and diabetes mellitus status at screening (Yes, No) subgroup are added for CogState GCCS endpoint; (3) subgroup categories of NYHA class at randomization are: I/II versus III/IV; (4) update Latin America to remove “including Central America” because no Central America countries participated in the study.

		10. Remove by-visit from average daily dose summary, remove one obsolete phrase, and update categories for summary. Add 2 class of HF and CV medications.		
Section 2.4.1: (1) Average daily dose summary is calculated for randomized treatment epoch, not by visit; (2) Categories for summary are updated per dry run review comment.
 
Section 2.4.2: Add SGLT2 class.

		11. Remove supportive analyses added in SAP Amendment V 3.0 that		Almost all randomized patients have at least one missing assessment during COVID-19

Date	Time point	Reason for update	Outcome for update	Section and title impacted (Current)
		
assess if there is a shift in change from baseline for those who have missing assessment(s) during COVID-19 pandemic.
 
12. (1) Shift table of SUVr positive/negative based on PET scan is removed since PET visual assessment of positive/negative is done only once at randomization; (2) correct analysis set used in SUVr supportive analysis; (3) Add one more supportive analysis for SUVr endpoint.
		
pandemic for CogState GCCS (Section 2.5.3), SUVr (Section 2.7.1.1), endpoints, therefore, the analyses are not meaningful and removed.
 
Section 2.7.1.1:
 
(1) Shift table of SUVr positive/negative based on PET scan is removed since PET visual assessment of positive/negative is done only once at randomization;
 
(2) PET substudy set instead of safety set is used SUVr supportive analysis;
 
(3) Supportive analysis of SUVr analysis excluding patients with no post-baseline SUVr assessments from analysis.

30-Jun-2022	Before DBL	
Handling of data collected on/after withdrawal of informed consent in the statistical analyses
 
Protocol amendment 2.0 is in effect when this SAP amendment takes place.
		
Handling of biological data and non-biological data collected on or after withdrawal of informed consent in statistical analyses are provided in Section 2.1.

Table of contents

Table of contents	11
List of abbreviations	13
1 Introduction	14
1.1 Study design.....	14
1.2 Study objectives and endpoints	16
2 Statistical methods.....	18
2.1 Data analysis general information	18
2.1.1 General definitions	19
2.2 Analysis sets	20
2.2.1 Subgroup of interest	21
2.3 Patient disposition, demographics and other baseline characteristics	23
2.3.1 Patient disposition	23
2.3.2 Demographic and baseline characteristics	23
2.3.3 Medical history.....	24
